2.10 Unscheduled Visits

An unscheduled visit may be performed at any time during the study at the subject's request or as deemed necessary by the site Investigator. The date and reason for the unscheduled visit will be recorded in the source documentation.

2.11 Replacement of Subjects

Replacement of subjects who have withdrawn or been withdrawn from the study will not be allowed to be replaced without prior approval from the sponsor and/or IRB.

2.12 Schedule of Visits and Procedures

	Visit #1	Visit #2 (optional)
Procedure	Biopsy	Follow Up 1 Week Post Biopsy (7-10 Days)
Pregnancy Verification*	X	
Biopsy	X	
Suture Removal		X
Photographs	X	X
Adverse Events Assessment	X	X

*Pregnancy verification required before biopsy only for women of childbearing potential.

2.13 Evaluation Methods

Skin Biopsies:

Biopsies will be obtained to examine the effects on the skin following radiofrequency treatments. Sections of skin will be removed using the punch biopsy technique to render a microscopic diagnosis. Each specimen will first be preserved with a fixative and then stained using Hematoxylin & Eosin, Verhoeff and Masson Red/Fast Green and/or nitroblue tetrazolium chloride (NBTC) staining methods. If using Hematoxylin & Eosin, Verhoeff and Masson Red/Fast Green staining, samples will be assessed and evaluated by the amount of collagen and elastin stained. If using NBTC staining, samples will be assessed and evaluated to differentiate between the blue-stained viable cells and the unstained thermally damaged cells. A report will be provided for each sample by the pathologist or the Investigator.

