1.2 Objectives

Primary Objective:

- Evaluate histological tissue response as seen in biopsies.

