2.0 PROTOCOL

2.1 Protocol Methodology and Analysis

Methodology:

Subjects are to be enrolled in this clinical study if they have completed their participation in the CYN20-FIRM-LIPO study. Up to 10 subjects will be enrolled at up to 4 study centers. Subjects will receive 2 biopsies, 1 biopsy in the treatment area on the flank and 1 biopsy on the contralateral side to serve as a control.

Analysis:

Upcoming generations are proving to have an interest in non-ablative aesthetic treatments and will drive demand for innovated products, procedures, and practice design.³ Due to this shift in patient base, practices need to evolve to adapt to the newer generational ideologies. There have been rapid advances in RF technology over the past few years and the nonsurgical treatment using this energy source offers great promise to our aging population.⁴ Radiofrequency technology for the treatment of abdominal wrinkles needs to be further investigated to optimize treatment parameters for safe and effective non-ablative aesthetic treatments.

Relevance:

Over time, skin structure degrades due to a variety of internal and external conditions. As enzymes break down collagen and elastin, skin loses its suppleness and becomes loose. UV exposure, diet, and smoking among other behaviors all contribute to the skin becoming lax. Body wrinkles, particularly on the abdomen, are a sign of aging and are also a prevalent concern with postpartum women or subjects who have lost weight. It is estimated that adult skin loses approximately 1% of its dermal collagen content on an annual basis due to increased collagen degradation and decreased collagen synthesis.² Radiofrequency, ultrasound, non-ablative fractional technology, and ablative technology have all been used to varying degrees of success. The limitations of current products on the market include different side effect profiles and modes of administration.

Testability:

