2.3 Subject Selection Criteria

Subjects will meet the criteria described below:

Inclusion Criteria:

- Subject has completed their participation in the CYN20-FIRM-LIPO study no more than 6 months prior.

Exclusion Criteria:

- The subject has not had any other treatment in the treatment area after their involvement in the CYN20-FIRM-LIPO study.
- The subject has any condition or is in a situation which in the investigators opinion may put the subject at significant risk, may confound study results or may interfere significantly with the subject's participation.

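### Section 2.13 fixes every specimen before staining yet reads NBTC as cell viability, and its *and/or* lets a biopsy pair go without any collagen or elastin stain

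*Protocol*

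**What the plan says.** The single objective in Protocol section 1.2 is "Evaluate histological tissue response as seen in biopsies". Section 2.1 allows up to 10 subjects at up to 4 centers, each with one biopsy in the treated flank and one on the other side as control. Under Testability, the same section says the histology is meant to confirm that the device acts safely and effectively on collagen in the dermis.

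Section 2.13 sets out the handling and the readings:

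- Order of handling: "Each specimen will first be preserved with a fixative and then stained".
- Choice of stains: Hematoxylin & Eosin, "Verhoeff and Masson Red/Fast Green and/or nitroblue tetrazolium chloride (NBTC) staining methods".
- Reading of the first group of stains: "samples will be assessed and evaluated by the amount of collagen and elastin stained".
- Reading of NBTC: "samples will be assessed and evaluated to differentiate between the blue-stained viable cells and the unstained thermally damaged cells".

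On timing, section 2.1 says "Subjects are to be enrolled in this clinical study if they have completed their participation in the CYN20-FIRM-LIPO study", and section 2.3 adds the limit "Subject has completed their participation in the CYN20-FIRM-LIPO study no more than 6 months prior". The visit schedule in section 2.12 has a biopsy visit and an optional follow-up. No device treatment is given in this study.

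**The concern.** Two features of section 2.13 work against the study's purpose.

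First, the order of handling conflicts with the meaning given to NBTC. The reading depends on some cells being alive at staining and others not, with heat as the reason for the difference. If all tissue has been fixed beforehand, heat is no longer the only explanation for a missing stain.

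Second, *and/or* makes the collagen and elastin stains optional. The choice of stain decides what the study measures, because histology is its only objective. A pair stained with NBTC alone would be fully compliant and would say nothing about collagen or elastin. Nothing in the protocol requires the same stains across subjects, across centers, or across the two specimens of one subject.

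At stake is whether each subject, who undergoes two punch biopsies, contributes to the question the biopsies are taken to answer.

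**Working it through.** The plan states no figure on this point, so the check is to set the provisions side by side.

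**1. Does fixation apply to NBTC specimens?** The fixative sentence in section 2.13 covers each specimen, places fixation first, and lists NBTC among the stains that follow. The protocol describes no unfixed or frozen handling. As written, NBTC tissue is fixed.

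**2. Can NBTC then be read as stated?** Section 2.13 uses the stain "to differentiate between the blue-stained viable cells and the unstained thermally damaged cells". That inference requires heat to be what separates stained from unstained cells. Fixation ends viability in treated and control tissue alike, so absence of stain has a second explanation that is present in every specimen. Whether any staining remains would depend on the fixative and the duration of fixation, and the protocol names neither. In either case an unstained area cannot be assigned to heat.

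**3. Can a pair lack collagen and elastin information?**

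| Stains chosen for the pair | Permitted by section 2.13 | Collagen and elastin reading |
|---|---|---|
| H&E, Verhoeff and Masson only | Yes | Yes |
| Both groups | Yes | Yes |
| NBTC only | Yes | None |

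The third row is compliant and gives none of the collagen evidence described in section 2.1 (Testability). With at most 10 subjects and 2 biopsies each, there are at most 10 × 2 = 20 specimens. The number of NBTC-only pairs may be anything from 0 to 10.

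**4. What does timing add?** The interval from last treatment to entry into this study is X + Y. X is the time from last treatment to completion of the parent study and is not stated. Y is the time from completion to entry, and section 2.3 limits it to 0 to 6 months. For assumed values of X:

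- X = 0 months: 0 to 6 months
- X = 1 month: 1 to 7 months
- X = 3 months: 3 to 9 months

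There is no minimum interval and no last-treatment date. Section 1.4 separates an immediate effect (collagen contraction) from a long-term one (wound healing with new collagen) but dates neither. A reading of thermal damage therefore fits the collagen question poorly, but the documents do not fix how long after treatment it is taken.

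**The case against.** The strongest objection is that the protocol never says fixation abolishes the NBTC stain. The fixative sentence may be a loose summary covering several methods, with stain-specific handling left to the laboratory. It is true that the step from fixation to loss of viability is general laboratory knowledge and not protocol text. But the sentence as written covers every specimen, and the meaning assigned to NBTC is the protocol's own. If the laboratory is meant to handle NBTC tissue differently, the protocol currently tells it otherwise.

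A second objection is that NBTC is optional, that this is described as a feasibility study, and that the objective is tissue response in general. Section 2.1 also mentions safety, for which a search for residual damaged cells could be useful. This stands in part: the defect does not touch the collagen and elastin stains where they are used. A safety use would still need an interpretable reading, and it would not replace the collagen evidence.

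Several stronger readings are tempting but not supported:

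- A reader might infer that fixed tissue would be reported as widespread thermal damage. Each subject has a contralateral control that passes through the same fixative, and an unstained control would tend to expose the artefact.
- A reader might infer that the biopsies are taken long after treatment, so that NBTC could not show any device effect. Only an upper limit from parent-study completion is given, so this is not shown for every subject.
- A reader might try to express the problem as lost power. The protocol gives no test, significance level, power or standard deviation, and no expected number of NBTC-only pairs. Such a figure would rest wholly on assumptions and would say nothing about fixation.

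**Conclusion.** The point holds in two parts. As section 2.13 is written, an unstained area on NBTC cannot be interpreted as thermal damage, because all tissue is fixed first. Separately, the protocol permits a subject's pair to be stained with NBTC alone, which yields no collagen or elastin information despite the purpose stated in section 2.1 (Testability). Timing is a supporting consideration only.

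The extent is bounded at 10 pairs, and the protocol does not say how many, if any, would be NBTC-only. The conclusion assumes that the fixative acts before the stain, as the sentence says, and that fixed cells are no longer viable. It does not extend to the collagen and elastin readings or to the study as a whole. The wording should be changed, because the change is cheap and a study of this size has few pairs to spare.

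**What to change.** In section 2.13, replace *and/or* with wording that makes the collagen and elastin stains mandatory for both specimens of every subject, and remove NBTC as a stand-alone option.

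Then settle NBTC in one of two ways:

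- Keep it only as an additional stain, and amend the fixative sentence so that the tissue set aside for it is exempt from fixation. This depends on the laboratory confirming that a 2 or 3 mm punch (section 2.7) can be divided between fixed and unfixed work, which the protocol does not show.
- If the punch cannot be divided, drop NBTC.

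Exempting the tissue removes the fixation conflict only. It does not make NBTC a measure of collagen, which is why the other stains must be mandatory in either case.

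The cost is a protocol wording change, submitted as an amendment, and one question to the laboratory. The downside is losing NBTC as a sole stain. No extra biopsy is needed.

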The improvement in the appearance of skin has been previously linked to a histological evaluation of the treatment area and can be used to verify an increase in collagen after a radiofrequency treatment. [name] in 2008 published an article titled *Tissue Tightening Technologies: Fact or Fiction* which discusses the link between changes in collagen and improvement in skin tightening, including wrinkles. The collection of biopsies will allow a histological evaluation of the treatment area to confirm the device is safely and effectively affecting the collagen in the dermis.

Compatibility:

Not applicable – feasibility study.

Predictive power:

While this study will observe the effects of the handpieces on the flanks, results could potentially be applied to a variety of body areas and other potential applications. Assuming that there is significant improvement, it would be appropriate to expect results in different areas where other products and devices have significant results.

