2.7 Biopsy Procedures

- Biopsy subjects will receive 2 biopsies, 1 in the treatment area and 1 on the contralateral side of the treatment area to serve as a control.
- A local anesthetic, such as lidocaine, will be injected to the area prior to biopsy.
- A 2 mm or 3mm punch biopsy (based on Physician assessment) will be taken.

- Sutures may be used to close the incision site.

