3.0 RISK MANAGEMENT

The Investigator in this clinical trial has been invited to participate based on his/her previous experience with the use of the system and/or similar systems and industry experience. Experience with biopsies is the most critical element in managing subject risk in this trial.

In addition, as with any study, there is a risk of bias. Objective evaluation methods will be used. The value of the compensation to the clinical investigator for conducting the study is not influenced by the study outcome.

All other known risks will be disclosed to the subject via the informed consent process. Since this is an elective procedure and the subjects are volunteers, it can be assumed that their signature on the informed consent is indicative of their agreement to accept the risks involved.

The risks to the subjects who participate in this study are the same as those for most subjects undergoing biopsies when enrolled in a non-ablative radiofrequency study.

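### Section 2.13 gives the histology readouts no unit, denominator or scale and lets specimen size, stain and reader vary, so a comparable treated-versus-control quantity is not secured

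*Protocol*

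**What the plan says.** The only objective, in Protocol section 1.2, is "Evaluate histological tissue response as seen in biopsies". Section 2.1 sets the size, "Up to 10 subjects will be enrolled at up to 4 study centers", and the pairing: "1 biopsy in the treatment area on the flank and 1 biopsy on the contralateral side to serve as a control". The same section says what the histology is for: it "can be used to verify an increase in collagen after a radiofrequency treatment".

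Section 2.13 is where the measurement is described. Tissue is taken "to render a microscopic diagnosis" and then stained with a collagen and elastin set (Hematoxylin & Eosin, Verhoeff, Masson), with NBTC, or with both. For the first set, "samples will be assessed and evaluated by the amount of collagen and elastin stained". For NBTC, the reader separates viable cells from thermally damaged ones. Each sample receives its own report, written by either a pathologist or the investigator.

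Two other places bear on this. Section 2.7 leaves specimen size open: "A 2 mm or 3mm punch biopsy (based on Physician assessment) will be taken". Section 3.0 acknowledges a risk of bias and answers it with "Objective evaluation methods will be used".

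**The concern.** Verifying an increase in collagen is a quantitative and comparative aim. It needs a number per specimen that means the same thing on both sides of a subject. Section 2.13 does not define one. An amount without a unit or denominator could be a total over the specimen, a share of the area examined, or a reader's impression. The NBTC readout has no count, proportion or grade either.

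Three things that affect such a reading are left free within a pair: how much tissue is taken, which stains are applied, and who reads the slide. Section 2.13 does not say that the reader is unaware of which specimen is the treated one, and the reader may be the investigator. A treated-control difference could therefore reflect specimen size, stain choice or reader expectation instead of the device. Section 3.0 relies on objective methods to deal with that risk, and no section describes a method with that property.

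**Working it through.** The protocol states no power, effect size or variability, so there is no planned figure to reproduce. The check has two parts: what the text fixes, and how much the open specimen size could matter.

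**What is fixed and what is open**

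| Element | Protocol text | Fixed within a subject's pair? |
|---|---|---|
| Control specimen | Sections 2.1 and 2.7: contralateral side | Yes |
| Punch size | Section 2.7: 2 mm or 3 mm by physician assessment | No |
| Stain set | Section 2.13: collagen and elastin stains and/or NBTC | No |
| Collagen and elastin readout | Section 2.13: amount stained | No unit, denominator, depth or field rule |
| NBTC readout | Section 2.13: viable against damaged cells | No count, proportion or scale |
| Reader | Section 2.13: pathologist or investigator | No |
| Masking to side | Not mentioned | No |
| Result reported | Section 2.13: one report per sample | No treated-versus-control result named |

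Because the stain sets are joined by and/or, a specimen may be stained with NBTC alone and then have no collagen or elastin readout.

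**Effect of punch size on a raw amount**

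Inputs: diameters of 2 mm and 3 mm (section 2.7). Assumptions: both specimens have the same true stain density and the same depth.

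- Cross-section of a punch = π × (diameter/2)². For 2 mm: π × 1² = 3.14 mm². For 3 mm: π × 1.5² = 7.07 mm².
- Ratio of cross-sections, and of volumes at equal depth: (3/2)² = 2.25.
- Ratio of vertical section areas at equal depth: 3/2 = 1.5.

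Treated/control ratio when the device has no effect:

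| Treated, control | Raw amount, section area | Raw amount, volume | Stained fraction |
|---|---|---|---|
| 2 mm, 2 mm | 1.00 | 1.00 | 1.00 |
| 3 mm, 3 mm | 1.00 | 1.00 | 1.00 |
| 3 mm, 2 mm | 1.50 (+50%) | 2.25 (+125%) | 1.00 |
| 2 mm, 3 mm | 0.67 (−33%) | 0.44 (−56%) | 1.00 |

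The fraction column is constant because the tissue examined cancels: (density × area) / area = density.

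Matched punches remove the spurious within-subject difference. They do not put subjects on one scale. For the same true density difference d, the raw difference is d × tissue examined, so a 3 mm pair shows 1.5 to 2.25 times the raw difference of a 2 mm pair.

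**Number of specimens**

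10 subjects × 2 biopsies = 20 at most.

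**The case against.** The strongest defence is that this is a small feasibility study with a descriptive objective. The protocol states no hypothesis test or success criterion, and a pathologist's narrative can describe tissue response. How paired results are summarised commonly belongs in a statistical analysis plan, and slide-reading rules may sit in a pathology procedure that is not shown. Much of this stands: the absence of a mean, confidence interval or test is no fault of the protocol. It does not cover the measurement itself. Section 2.13 takes up that subject and leaves the unit, reader and stain open. An analysis plan cannot subtract narratives or supply a stain that was not applied. Section 2.1 also goes beyond description when it speaks of verifying an increase.

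Several stronger readings are tempting, and the documents do not support them.

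- A reader might infer that stain amount is the only readout. Section 2.13 also has the NBTC readout, which is equally unquantified.
- A reader might infer that the amount is deliberately un-normalised. The text is silent: it neither gives nor excludes a denominator.
- A reader might infer that no treated-minus-control comparison is possible. The design provides the control, and two reports from one subject can be set side by side. If punch, stain and reader happen to match, a difference may be formed.
- A reader might set the size artefact against the roughly 1% annual collagen loss in section 2.1. That figure describes ageing. It is neither an expected device effect nor a scale for the treated-control difference.

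**Conclusion.** The point holds in this form: section 2.13 does not secure a comparable treated-versus-control quantity, and it does not substantiate the objective evaluation that section 3.0 offers against bias. It should be corrected because the study's one objective depends on this readout.

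The factor of 1.5 to 2.25 is conditional. It requires that a raw total is read, that the two punches of a subject differ, and that depth and true density are equal. The upper end applies only to a whole-specimen total; for a vertical section the factor is 1.5. Nothing in the protocol says that sizes will differ within a subject, so the range shows what the text permits and is not a forecast. The possible influence of reader and stain choice cannot be sized from the document.

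The phrase about a microscopic diagnosis is loose wording, but removing it would change no result.

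**What to change.** In section 2.13:

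1. For specimens with Masson and Verhoeff stains, record the percent of examined dermal area staining for collagen and for elastin, using one fixed threshold, a fixed number of fields and the same dermal depth.
2. For NBTC specimens, record the proportion of viable cells among the cells examined.
3. Use the same stain set and the same existing reader for both specimens of a subject, with slides coded so that the side is hidden.
4. Name each subject's treated-minus-control difference as the study result, listed per subject. Any further summary can be left to the analysis plan.

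Section 3.0 can then refer to section 2.13 for its statement on objective methods. Because a fraction does not depend on specimen size, the physician's choice of punch in section 2.7 need not change.

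The cost is protocol wording, slide coding, and more reading or image-analysis time on at most 20 specimens. No new biopsy or additional reader is needed. The protocol names no image-analysis facility, and section 7.0 says that no other institution takes part, so the sponsor should confirm that the existing reader can make the measurement.

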2.5 Informed Consent Process and Enrollment

Subjects will be asked to review the post treatment instructions prior to signing the informed consent form and their involvement in the study. Subjects will be informed of standard COVID-19 procedures that adhere to federal and state guidelines at this time. Subjects will be de-identified through their subject identification number, which will be stored in a secure location. Subject identification numbers will be generated chronologically and assigned only to subjects who have met all the study selection criteria and have signed the informed consent form. The informed consent will be obtained prior to a subject's involvement in any study related procedures. A subject will be considered enrolled in the study once they have signed the informed consent form.

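### Section 2.13 lets the Investigator report the biopsies without masking to side, so the treated-versus-control reading behind the only objective may be made by someone who knows which specimen was treated

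*Protocol*

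**What the plan says.** The only objective in section 1.2 is "Evaluate histological tissue response as seen in biopsies". Section 2.1 sets the scale, "Up to 10 subjects will be enrolled at up to 4 study centers", and the comparison, "1 biopsy in the treatment area on the flank and 1 biopsy on the contralateral side to serve as a control".

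Section 2.13 names the stains and what is read from them. With the Hematoxylin & Eosin, Verhoeff and Masson stains, "samples will be assessed and evaluated by the amount of collagen and elastin stained". With the NBTC stain, the purpose is "to differentiate between the blue-stained viable cells and the unstained thermally damaged cells". On who reads, it says: "A report will be provided for each sample by the pathologist or the Investigator". It does not say which of the two reads in which case, and it does not require that the reader be unaware of side.

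On coding, section 2.5 says "Subjects will be de-identified through their subject identification number". Section 3.0 acknowledges that bias is a risk, promises objective methods of evaluation, and notes that the Investigator's compensation does not depend on the outcome.

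**The concern.** The Investigator is the person at the site most likely to know which flank was treated, and section 2.13 makes that person an acceptable reader of the primary outcome. The Testability paragraph of section 2.1 says what the reading is expected to show: histology "can be used to verify an increase in collagen after a radiofrequency treatment". Section 2.13 gives no grading scale or image-analysis rule for judging the amount of stained tissue, so judgement can enter.

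A reader who knows the side and expects more collagen there can read the treated specimen more favorably. At stake is whether a treated-versus-control difference reported from this study can be attributed to the treatment rather than partly to the reader. This matters beyond the study itself, because section 2.1 contemplates carrying the results over to other body areas.

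**Working it through.** The protocol states no figure on this point, so there is none to reproduce. The check sets the relevant sections side by side and then counts what is exposed.

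**1. Can the reader know the side?**
- Sections 2.6 and 2.7: the biopsy area is identified and may be marked. One specimen then comes from the treated area and one from the opposite side, with punch size chosen by the physician. These steps are written in the passive, but they take place at the site.
- Section 3.0 treats the Investigator's experience with biopsies as central to managing risk, which fits the Investigator being involved in the procedure.
- Section 2.13: the Investigator may then report the specimens.

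An Investigator who reads can therefore be expected to know the side. What a pathologist would know is not stated.

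**2. Does anything conceal the side?**
- Section 2.5: there is one identification number per subject. Both specimens of a subject share it, so it cannot hide which is which.
- Section 13.0: the code number on study records serves confidentiality and is also per subject.
- Section 3.0: the promise of objective evaluation names no method, and compensation that is independent of outcome is not masking.
- No section in the available text mentions masking, specimen codes that hide side, or reading order.

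**3. Does pairing protect the comparison?** Write the treated reading for subject *i* as T*i* + *b*, where *b* is the shift caused by knowing the side, and the control reading as C*i*. The paired difference is

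(T*i* + *b*) − C*i* = (T*i* − C*i*) + *b*.

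Pairing removes what is common to both flanks of a subject. It leaves *b* in every difference, so the mean difference is also shifted by *b*, whatever the number of subjects.

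**4. How much of the data is exposed?**
- Section 2.1: up to 10 subjects × 2 biopsies = up to 20 specimens (10 treated, 10 control).
- If 10 subjects were spread as evenly as possible over 4 centers (an assumption), 10/4 = 2.5. Each center would have 2 or 3 subjects, that is 2 × 2 = 4 or 3 × 2 = 6 specimens.
- With uneven enrollment, an enrolling center could have from 1 × 2 = 2 to 10 × 2 = 20 specimens.

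These are counts of specimens, not a measure of bias. The documents contain nothing from which *b* could be derived.

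**The case against.** The strongest reply is that this is a feasibility study with a descriptive objective, no stated test and no success threshold, so nothing in the document is made invalid. That stands, and it is why the point is a cheap improvement and not a fatal flaw.

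A second reply is that section 2.13 only says who issues a report. It does not say the reader is unmasked, and a pathologist might in practice not know the side. That is also true, and the claim is limited accordingly: the text permits an unmasked reading and does not require one. But the section does settle who may read, and it admits the Investigator without condition. Following it exactly can produce a biased comparison. Masking also has to be in place when specimens are labelled, so it cannot be left to the analysis.

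Third, section 6.0 was not in the text available here, and a reading laboratory could be named there. For that reason nothing here rests on the absence of an outside laboratory. Such a laboratory would not by itself mask the reader, and the option for the Investigator to report would remain.

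Finally, a coded label may not fully mask someone who took both biopsies. Section 2.7 allows two punch sizes, and if they differed within a pair the size could hint at side. This is a real limit on the remedy, but it arises only where sizes differ within a pair.

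**Conclusion.** The concern holds. As written, section 2.13 allows the treated-versus-control histology, the sole basis for the only objective, to be read by someone who knows the side and the expected direction, and nothing elsewhere in the available text prevents it. Up to 20 specimens (10 pairs) are exposed. The size of the bias is unknown.

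The conclusion assumes that an Investigator who reports specimens knows which flank they came from, which sections 2.6, 2.7 and 3.0 make likely but do not state outright. The consequence is limited interpretability of a descriptive result, not failure of a stated test. It should be fixed before specimens are read, because readings made with the side known are hard to repair afterwards.

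**What to change.** In section 2.13, keep the sentence naming the reader and add after it:

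> Each specimen will be labelled with a code that does not show side or treatment. The reader (pathologist or Investigator) will be masked to side. The code will be assigned and held by existing study staff who do no reading, and will be broken only after all readings are recorded.

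In section 3.0, keep the promise of objective evaluation and add:

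> Histology will be read masked to side, as described in 2.13.

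A minor optional addition to section 2.13 is that the same reader reports both specimens of a subject. Nothing in the protocol suggests that pairs would be split.

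**Cost.** Coded labels for up to 20 specimens (4 or 6 per center if spread evenly over 4 centers) and a key to keep. No reader, biopsy or visit is added, and both readers named in section 2.13 remain eligible. Section 11.0 already refers to designated study staff besides the Investigator, though for adverse event review, so the sponsor should confirm that each center has someone who does no reading to hold the key. The downsides are this small labelling task and the loss of unmasked local reading. Where the two specimens of a pair differ visibly in size, masking is more secure if the reader is the one who did not take them.
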